8.1.2. Secondary Immunogenicity Endpoint

To address the second objective of the study the binding antibody responses of ARCT-021 will be compared to placebo for the priming vaccination period. SARS-CoV-2 binding antibodies

(BAbs) will be tested using an MSD multiplex assay which measures total immunoglobulin G (IgG) against the full-length spike, RBD and N antigens of the Wuhan strain.

- IgG measured against the Nucleocapsid (N) antigen of the Wuhan strain SARS-CoV-2 (VAC72_ECL_CoV-2_N)
- IgG measured against the RBD antigen of the Wuhan strain SARS-CoV-2 (VAC72_ECL_CoV-2_RBD)
- IgG measured against the Spike antigen of the Wuhan strain SARS-CoV-2 (VAC72_ECL-CoV-2_S)

Similar estimands will be used as for the neutralizing antibody (NAbs).

8.2. Analysis of Immunogenicity Primary and Secondary Endpoints

8.2.1. Analysis of primary and secondary immunogenicity endpoints

Total NAbS and BAbS titers will be summarized using descriptive statistics (number of subjects (n), median, minimum and maximum) by each time point in priming vaccination period (Baseline, Days 14, 28, 42, 56, 208) and booster vaccination period (Day 208, 236, Early Termination). Summaries of priming vaccination and booster vaccination periods based on their corresponding mITT and PP analysis sets will be presented separately using the applicable treatment groups (Table 4-1). For the analysis of booster mITT analysis set, summary tables with active boosters pooled (as presented in Table 4-1; e.g., A1, A2, B1, B2, etc.) will also be presented.

The following statistics will be provided in the summary tables and/or figures:

- Geometric mean titer (GMT) with corresponding 95% CI will be provided at each time point. The 95% CIs will be calculated based on the t-distribution of the log-transformed values then back transformed to the original scale for presentation. GMT level and corresponding 95% CI will be plotted at each timepoint in priming vaccination period for mITT analysis set. Plots of the reverse cumulative distribution curves also will be provided by treatment group and visit in priming vaccination period for mITT analysis set.
- Geometric mean fold rise (GMFR) with corresponding 95% CI will be provided at each post-baseline timepoint over baseline. The 95% CIs will be calculated based on the t-distribution of the log-transformed values then back transformed to the original scale for

presentation. GMFR and corresponding 95% CI will be plotted at each timepoint in priming vaccination period for mITT analysis set.

- The number and percentage of subjects with fold-rise ≥ 2 and fold-rise ≥ 4 from baseline (Seroconversion) at each post baseline time points will be tabulated with the 2-sided 95% CI using the Clopper Pearson method at each post-baseline timepoint.
- Seropositivity at a participant level is defined as any detectable antibody level above the lower limit of quantification (LLOQ) for the specific assay and antibody measured at timepoints after baseline. Seropositivity rates will be provided with 2-sided 95% CI using the Clopper-Pearson method at each post-baseline time point.

The definition of seroconversion/seropositivity may depend on assay-specific performance characteristics. The conventions are as follows:

- Seropositivity is defined as any detectable antibody level above the lower limit of quantification (LLOQ) for the specific assay and antibody measured.
- For the MesoScaleDiscovery nucleocapsid antibody test (VAC72_ECL_CoV-2_N), seroconversion will be assessed in 2 ways:
 - Defined as a 2- or 4-fold increase above baseline (pre-vaccination antibody levels).
 - Based on detection of an antibody level ≥ 5000 AU/mL, a threshold associated with evidence of SARS-CoV-2 clinical infection/viral exposure.
- For all other assays and antibodies, seroconversion will be defined as a 2- or 4-fold increase above baseline (pre-vaccination antibody levels).
- For seronegative individuals, one half of the value of the LLOQ will be calculated as the baseline antibody level

The LLOQs for each assay are shown below.

- VAC62_MN_CoV-2 (IU/mL): 7.8431372549
- VAC72_ECL_CoV-2_N (BAU/mL): 0.06372
- VAC72_ECL_CoV-2_RBD (BAU/mL): 0.5168

VAC72_ECL_CoV-2_S (BAU/mL): 0.20723 The GMT will be calculated using the following formula:

$$GMT = e^{\left\{ \frac{\sum_{i=1}^n \log_e(t_i)}{n} \right\}}$$

where t_1, t_2, \dots, t_n are observed immunogenicity titers for n participants.

The GMFR measures the changes in immunogenicity titers within participants. The GMFR will be calculated using the following formula:

$$GMFR = e^{\left\{ \frac{\sum_{i=1}^n \log_e \frac{v_{ij}}{v_{ik}}}{n} \right\}} = e^{\left\{ \frac{\sum_{i=1}^n (\log_e v_{ij} - \log_e v_{ik})}{n} \right\}}$$

where, for n participants, v_{ij} and v_{ik} are observed immunogenicity titers for participant i at time points j and $k=0$ (Baseline, Day 0).

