Screening (up to 14 days): At Screening, individuals willing to participate in the study will undergo informed consent followed by an interview (to review medical history, current symptoms, COVID-19 exposures, medications, recent vaccinations, and availability for study procedures), urine test for drugs/alcohol, physical examination, measurement of vital signs (systolic and diastolic blood pressure, heart rate, respiratory rate, and pulse oximetry), body temperature, height and weight, and pregnancy testing for participants of childbearing potential. At the completion of Screening, the Investigator will review all data for determination of participant eligibility. Eligible participants will be enrolled and assigned a dedicated participant ID number.

Notes: Exposure to COVID-19 is defined as a participant who has had close contact (within 6 feet [2 meters] for a total of 15 minutes or more) to a person with laboratory-confirmed COVID-19 (or clinically compatible illness) or to a person who has tested positive for COVID-19 (laboratory confirmed) but has not had any symptoms. This is irrespective of whether the person with COVID-19 or the contact was wearing a mask or whether the contact was wearing respiratory personal protective equipment (PPE).

If, during Screening, there is uncertainty regarding past exposure to SARS-CoV-2, a specimen may be collected at the Investigator's discretion, for testing for SARS-CoV-2 infection and/or antibody at a local laboratory.

Visits: All enrolled participants in Study Groups 1, 2, and 3 may have up to 12 scheduled visits, including Screening, Dose 1 Administration (Day 0), Follow-up 1 and 2 (Day 7 and Day 14), Dose 2 Administration (Day 28), Follow-up 3 and 4 (Day 35 and Day 42), Follow-up 5 (Day 56), Booster Administration (Day 208), Booster Follow-up 1 (Day 215), Booster Follow-up 2 (Day 236), and Early Termination Visit.

For participants in Study Group 4 who re-enroll in the study, clinic visits representing Dose 1 Administration (Day 0), Follow-up 1 and 2 (Day 7 and Day 14), Dose 2 Administration (Day 28), Follow-up 3 and 4 (Day 35 and Day 42), Follow-up 5 (Day 56) will be performed again, and, as such, may have up to 19 scheduled visits. Informed consent will be obtained again for these participants prior to re-enrollment into the study.

Administration Visits: At each Dose and Booster Administration visit, participants will undergo an interview, pregnancy testing (if the participant is a woman of childbearing

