Seroconversion (SC) is defined with as ≥ 2 -fold and also ≥ 4 -fold GMFR. Seropositivity is defined as those participants with undetectable antibody responses at baseline whose antibody responses become detectable at time points after baseline. The number and percentage of participants with ≥ 2 - and 4-fold GMFR from baseline and with seropositivity will be provided with 2-sided 95% CI using the Clopper-Pearson method at each post-baseline time point. The common difference of seroconversion rate and 95% CI between each vaccine dose group and the placebo will be estimated in the mITT using the Cochran–Mantel–Haenszel (CMH) method with stratification factors for each time point from Day 28 and later timepoints as specified in the SAP.

Arcturus Therapeutics, Inc.
Protocol ARCT-021-04, Version 6.0

ARCT-021
09 March 2022

Cell-mediated response for both Th1 and Th2 pathways will be assessed by measuring intracellular cytokine expression by flow cytometry of PBMCs isolated from whole blood and summarized by Study Group and Age Cohort in the CMI analysis set. Further details are described in the SAP.

Exploratory analyses of antibody responses and CMI will be described in the SAP prior to analysis. Additional subgroup analyses are described in the SAP.

Interim Analyses:

Three interim analyses will be performed.

- The first interim analysis will focus on safety and will evaluate available safety data for all participants who were initially enrolled as of 05 February 2021 when they have completed Day 7 or Early Termination visit procedures.
- The second interim analysis will evaluate available safety and immunogenicity data for all participants who were initially enrolled as of 05 February 2021 when they have completed Day 28 or Early Termination visit procedures.
- The third interim analysis will evaluate available safety and immunogenicity data for all participants when they have completed Day 56 or Early Termination visit procedures.

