4.1.2 Exclusion Criteria

Participants meeting any of the following criteria will be excluded from the study:

Medical Conditions

1. Individuals with a history of laboratory-confirmed SARS-CoV-2 infection or clinically diagnosed COVID-19 disease.
2. Individuals at high risk for severe COVID-19, including those with any of the following risk factors:
 - a. Individuals with a history of malignancy EXCEPT:

- i. Malignancy with low potential risk for recurrence after curative treatment (eg, history of childhood leukemia) or metastasis (for example, indolent prostate cancer) in the opinion of the Investigator
- ii. Adequately treated non-melanoma skin cancer or lentigo maligna without evidence of disease
- iii. Adequately treated uterine cervical carcinoma in situ without evidence of disease
- iv. Localized prostate cancer
- b. Chronic kidney disease Stage 3 or worse defined as estimated glomerular filtration rate $<60 \text{ mL/min}/1.73 \text{ m}^2$)
- c. Chronic obstructive pulmonary disease, cystic fibrosis, pulmonary fibrosis
- d. Cardiovascular conditions INCLUDING:
 - i. Hypertension uncontrolled for age according to the Eighth Joint
 - ii. National Committee guidelines ([James 2014](#))
 - iii. Congestive heart failure by New York Heart Association classification ≥ 2 ([Dolgin 1994](#))
 - iv. Recent (within 6 months prior to first study vaccination) exacerbation of coronary artery disease as manifested by cardiac intervention, addition of new cardiac medications for control of symptoms, or unstable angina
 - v. Cardiomyopathy
 - vi. Pulmonary hypertension
- e. Immunocompromised state from solid organ transplant
- f. Obesity (body mass index $\geq 30 \text{ kg/m}^2$)
- g. Sickle cell disease or other hemoglobinopathies
- h. Has smoked within the past 1 year. This includes vaping, tobacco, and marijuana products.
- i. Type 2 diabetes mellitus with glycosylated hemoglobin $\geq 8\%$ within the past 2 months

3. Individuals with severe and/or uncontrolled cardiovascular disease, respiratory disease, gastrointestinal disease, liver disease, renal disease, endocrine disorder, and neurological illness, as judged by the Investigator (mild/moderate well-controlled comorbidities are allowed).

Diagnostic Tests

4. Individuals with a positive test for human immunodeficiency virus (HIV), hepatitis B surface antigen, or hepatitis C virus antibodies (HCV Abs) at Screening.

Medical Conditions

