6.1. Demographics

Descriptive statistics will be calculated for the following continuous demographic and baseline characteristics: age (years), weight (kg), height (cm), body mass index (BMI) (kg/m²). The number and percentage of participants will be provided for categorical variables such as age group, sex, race, ethnicity, country, site, baseline SARS-CoV-2 serostatus (positive/negative/missing) defined by nucleocapsid testing at Day 0, and evidence of viral shedding as measured by a saliva RT-PCR test at Baseline.

Baseline SARS-CoV-2 serostatus is defined as SARS CoV-2 nucleocapsid (N) antibody level of greater or equal to 5000 (AU/mL). This threshold is defined by BioA laboratories based on levels for a clinical definition of PCR-confirmed COVID-19 infection.

The number and percentage of participants will be summarized by site and by stratification factor at randomization (i.e., ≥ 18 to <56 years; ≥ 56 years) separately based on the Safety set for the priming vaccination period, re-enroll subjects, and booster vaccination period.

Summaries will be provided separately based on the Safety set, mITT set, PP set, mITT-CMI subset by study treatment group. The summaries will be repeated by study treatment group for re-enrolled subjects based on Safety set and for the booster vaccination period based on the Booster Safety set, Booster mITT set, Booster PP set, Booster mITT-CMI subset. Summary of demographics by ≥ 18 to <65 years vs. ≥ 65 years will also be provided for the priming vaccination period.

For screened failure participants, age (years), gender, race and ethnicity will be presented in a listing.

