8.2.2. Supportive Analyses of Primary and Secondary Immunogenicity Endpoints

8.2.2.1. Supportive Analyses of Estimand 2

To assess the magnitudes of the differences between the treatment groups (ARCT-021 vs. Placebo) in SARS-CoV-2 neutralizing antibody (NAbs) and SARS-CoV-2 binding antibody (BAbs) endpoints, an analysis of covariance (ANCOVA) model will be fitted to the natural log transformed neutralizing antibody titers measured against SARS CoV 2 with terms for treatment group, age group (≥ 18 to < 56 and ≥ 56 years) (stratification factor at randomization) and natural log baseline titer by each post-vaccination immunogenicity visit. No imputation of missing data will be done.

The geometric least squares mean (GLSM) and corresponding 2-sided 95% CI for the antibody titers for each treatment group will be provided by visit. The GLSM and corresponding 95% CI results in log-transformed scale estimated from the model will be back-transformed to obtain these estimates in the original scale. Geometric mean ratio (GMR), estimated by the ratio of GLSM and the corresponding 2-sided 95% CI will be provided to assess the treatment difference between ARCT-021 group vs. placebo group at each visit.

ANCOVA analyses will be performed for the priming vaccination period on mITT analysis set only.

8.2.2.2. Supportive Analyses of Estimand 3

The common difference of seropositivity and seroconversion rates and 95% CIs between each vaccine dose group and the placebo will be estimated using the Miettinen-Nurminen method with age group (≥ 18 to < 56 and ≥ 56 years) as stratification factor for each time point.

Miettinen-Nurminen analyses will be performed for the priming vaccination period on mITT analysis set only.

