13.5. Appendix 3: Estimands and Intercurrent Events

Possible intercurrent events are presented in the table below.

Table 13-3 **Intercurrent Event Types**

Label	Intercurrent Event Type
IcEv1 (Death)	Death due to any cause (including pneumonia) other than COVID-19.
IcEv2 (Missed dose)	Does not receive the second vaccination at Day 28 where second vaccination assigned was ARCT-021 or does not receive booster vaccination at Day 208 where booster vaccination assigned was active ARCT booster. It is not necessary to exclude placebo missed second doses as there is no impact.
IcEv3 (Immune-modifying)	Use of immune-modifying drugs or non-study vaccines which interfere with immunogenicity. Immune-modifying drugs will be determined from a medical review of medications taken during the study.
IcEv4 (Early infection)	
Priming vaccination period: Antigens or antibodies indicating exposure to SARS-CoV-2 prior to vaccination or early infection before Day 7. (This IcEv is particularly relevant to assessing immunogenicity.) Early infection is defined as follows:
 
 ○ Positive PCR saliva test at baseline OR ○ Positive PCR test at any time up to 7 days post-baseline OR ○ Positive SARS-CoV-2 baseline serostatus 
Booster vaccination period: Antigens or antibodies indicating exposure to SARS-CoV-2 prior to vaccination or early infection before Day 7 post booster vaccination. (This IcEv is particularly relevant to assessing immunogenicity.) Early infection for different boosters is defined as follows:
 
 ○ Positive PCR saliva test on Day 208 OR the booster vaccination OR ○ Positive PCR test at any time up to 7 days post-booster vaccination
IcEv5 (Study infection)	Develops COVID-19 or asymptomatic SARS-CoV-2 infection on or after Day 7. (This IcEv is particularly relevant to immunogenicity and CESI events.). Study infection is defined as COVID-19 infection recorded on the adverse event CRF page with start date on or after Day 7. The following AE preferred terms will be considered: Asymptomatic COVID-19, COVID-19, Suspected COVID-19. Positive MSD nucleocapsid antibody value of 5000 AU/mL or higher at any point after baseline (with start date on or after Day 7) will also be considered as on-study infection.

Attributes for the primary safety estimands with strategies for IcEvs are presented in Table 13-4 below.

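### The SAP's seropositivity rate has no baseline condition, so antibody already present at Day 0 counts as positive in every arm and dilutes the supportive comparison with placebo

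*SAP*

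**What the plan says.** **Entry.** Protocol 4.1.2, criterion 1, excludes "Individuals with a history of laboratory-confirmed SARS-CoV-2 infection or clinically diagnosed COVID-19 disease". Serology is not mandatory at Screening. If past exposure is uncertain, the Protocol Synopsis says that "a specimen may be collected at the Investigator's discretion, for testing for SARS-CoV-2 infection and/or antibody at a local laboratory"; the matching text in Protocol 6 mentions RT-PCR only.

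**Removal.** SAP Table 13-3 defines early infection in the priming period by any of three findings: a positive saliva PCR at baseline, a positive PCR up to 7 days later, or positive baseline serostatus. SAP 6.1 sets serostatus at N antibody of 5000 AU/mL or more and explains: "This threshold is defined by BioA laboratories based on levels for a clinical definition of PCR-confirmed COVID-19 infection". Spike, RBD and neutralizing results at Day 0 remove nobody.

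**Definition.** SAP 8.2.1: "Seropositivity at a participant level is defined as any detectable antibody level above the lower limit of quantification (LLOQ) for the specific assay", measured after baseline. The protocol has three versions:
- Synopsis, Immunogenicity Analyses: "Seropositivity is defined as those participants with undetectable antibody responses at baseline whose antibody responses become detectable at time points after baseline".
- Section 7.6.4.2: a move from below to at or above the limit, or a fourfold criterion where titers pre-exist.
- Table 7-4: a detectable level above the LLOQ, with no baseline condition, as in the SAP.

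SAP 11, item 2, prints the 7.6.4.2 text beside the new one and gives clarification of the clinical definition as the reason.

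**Use.** Rates get Clopper-Pearson intervals. SAP 8.2.2.2 adds: "The common difference of seropositivity and seroconversion rates and 95% CIs between each vaccine dose group and the placebo will be estimated", by the Miettinen-Nurminen method stratified by age group, in the mITT for the priming period. SAP 8.4 lists these tables for both the neutralizing and the binding antibody.

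**The concern.** A seropositivity rate compared with placebo will be read as the share of people whom vaccination made positive. Under the SAP definition it is instead the share who are positive at a visit, for whatever reason. A placebo recipient with antibody from an undiagnosed infection is counted as positive at each visit where the level stays above the LLOQ, and so is a vaccine recipient who did not respond.

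The Synopsis and Section 7.6.4.2 each guard against this, by different means. The SAP has neither guard, and SAP 1 says that the SAP prevails where the two documents differ. No table in SAP 8.4 limits the rate to participants negative at Day 0, and seropositivity is specified only at post-baseline visits. At stake are the level of the rate in every arm and the size of the supportive difference from placebo.

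**Working it through.** The documents contain no figure for the share positive at Day 0 and no expected seropositivity rate, so there is no plan figure to reproduce. The check is algebra plus an illustration.

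**Inputs**
- f: share of analysed participants in an arm already above the LLOQ for the assay at Day 0, not removed as early infection, and still above it at the visit. Assumed, shown as a range. Randomization makes f equal across arms on average.
- pv, p0: rates of becoming positive among participants below the LLOQ at Day 0. Assumed at 90% and 2%. The 90% echoes Protocol 1.6, which reports fourfold spike seroconversion in more than 90% after single 5 µg doses, but that is a different measure. The 2% is a round number.

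**SAP rule**
- vaccine = f + (1 − f)·pv
- placebo = f + (1 − f)·p0
- difference = (1 − f)·(pv − p0)

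The rate rises by f(1 − pv) in a vaccine arm and by f(1 − p0) on placebo, so mostly on placebo.

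| f | Vaccine | Placebo | Difference (points) |
|---|---|---|---|
| 0 | 90.0% | 2.0% | 88.0 |
| 5% | 90.5% | 6.9% | 83.6 |
| 10% | 91.0% | 11.8% | 79.2 |
| 20% | 92.0% | 21.6% | 70.4 |

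For f = 10%: 0.10 + 0.90 × 0.90 = 0.910; 0.10 + 0.90 × 0.02 = 0.118; 0.910 − 0.118 = 0.792.

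With a weaker response (pv = 50%, p0 = 0), f = 5% gives 52.5% against 5%, a difference of 47.5 points instead of 50; f = 20% gives 60% against 20%, a difference of 40.

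**Head count.** Protocol 1.5 gives 579 enrolled; 579/4 is about 145 per group. At f = 10%, about 14 placebo participants would be counted as positive for antibody present before the first injection.

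**Would the Synopsis rule alone repair it?** Not fully. SAP 4 makes all participants of the group in the analysis set the default denominator. If baseline-positives stay in the denominator but cannot count as positive, the rates are (1 − f)·pv and (1 − f)·p0. At f = 10% these are 81.0% and 1.8%: the placebo rate is no longer inflated, but the difference is again 79.2. Only restricting the denominator to baseline-negatives returns 90%, 2% and 88 points.

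**The case against.** The strongest reply is that little depends on this rate. The endpoint tables list GMT or GMC, GMFR, the ratio to placebo and fold-rise seroconversion; seropositivity is an added rate, and its comparison with placebo is labelled supportive. Protocol 7.2 plans no hypothesis testing. This stands and keeps the point minor.

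A reader might infer that pre-existing antibody counts as response on the primary endpoint. The documents do not support that: seroconversion and GMFR are taken relative to each participant's own baseline, and the ANCOVA adjusts for log baseline titer.

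A reader might also infer that the N threshold is the only removal rule. It is not: PCR-positive participants at baseline or up to 7 days later are removed too. The threshold stands alone only for past, PCR-negative infection.

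Nor did the SAP quietly drop an agreed definition. Protocol Table 7-4 already had the same wording, and SAP 11 shows the change from 7.6.4.2. What stands is that the protocol disagrees with itself, and that calling the change a clarification does not say that a measure of response became a measure of prevalence.

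The size of f is unknown. The fourfold limb in 7.6.4.2 allows for pre-existing titers but does not show that they are common. The low binding-assay LLOQs do not show it either, and the N cut-off (AU/mL) cannot be set against the N assay's LLOQ (BAU/mL) because no conversion is given.

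Some baseline information is planned: titers are summarized at Baseline, N serostatus is tabulated, and a baseline panel of the reverse cumulative curves, if drawn, would show f roughly. None of these gives the rate among baseline-negatives.

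**Conclusion.** The point holds as a minor one. Unchanged Day 0 antibody raises the supplementary seropositivity rate in every arm and multiplies the expected difference from placebo by (1 − f). With assumed rates of 90% and 2%, the difference falls from 88 points to 83.6 at f = 5% and to 79.2 at f = 10%. This rests on equal f across arms and on these participants staying above the LLOQ; if some fall below it, the effect is smaller. If f is near zero, almost nothing changes.

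One might infer that the rule flatters the vaccine or distorted dose selection. On average the contrast with placebo is pulled toward no difference, and the evidence that Protocol 1.6 cites for the 5 µg choice is fold-rise seroconversion and reactogenicity, not seropositivity.

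**What to change.** In SAP 8.2.1, 8.2.2.2 and Table 13-6, report the seropositivity rate, its Clopper-Pearson interval and the Miettinen-Nurminen difference among participants below the LLOQ at Day 0 for that assay. This denominator is a recommendation: the Synopsis says who counts as seropositive but does not restrict the denominator.

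Add a row with the number at or above the LLOQ at Day 0, by group and assay. Use the same boundary at Day 0 and afterwards, since SAP 8.2.1 says above the limit and Protocol 7.6.4.2 says at or above it. Align the Protocol Synopsis, Table 7-4 and 7.6.4.2 with SAP 8.2.1, and have SAP 11 give the reason for the definition chosen. Leave the fold-rise endpoints unchanged. If the change is made after unblinding, label the restricted rate as post hoc.

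The Day 0 samples are already in the schedule, so the cost is wording, a denominator and one table row. Intervals for this rate widen slightly: at the same observed rate, by roughly 1/√0.95 = 1.03 at f = 5% and 1/√0.90 = 1.05 at f = 10%.
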